Antibiotic-resistant bacteria are becoming more common and constitute one of the biggest threats to our future health [1, 2]. To slow down this development, it is important not to prescribe antibiotics unnecessarily [3]. Pharyngotonsillitis (sore throat) is one of the most common causes of antibiotic prescribing in primary health care centres (PHCCs) [4, 5]. In the clinical everyday life, general practitioners (GPs) experience uncertainty about the treatment of patients with pharyngotonsillitis [6], and adherence to guidelines on diagnostics and treatment of pharyngotonsillitis needs to be improved [4, 7]. The single most important rule-of-thumb in primary care is to normally only prescribe antibiotics for pharyngotonsillitis when a positive rapid antigen detection test (RADT) for beta-haemolytic streptococci group A (GAS) is presented [8, 9].

It is important for GPs to have the opportunity to reflect on their own antibiotic prescribing, to have regular interdisciplinary discussions at the PHCC about antibiotics and guidelines to increase knowledge and understanding of the guidelines and thus feeling confident in the clinical everyday life [10-14]. Structural factors at the PHCC such as the manager's involvement and nurses' work on telephone counselling and on triage reception are also important in achieving a rational use of antibiotics [10]. Antimicrobial Stewardship Programs (ASP) are structured multifaceted interventions to reduce unnecessary antibiotic use and have in many cases led to more rational use of antibiotics within inpatient care [15-17]. There is largely no evidence showing which ASPs are effective in PHCCs, at least from a Swedish perspective since we have a comparatively low rate of antibiotic prescribing [17, 18]. Since pharyngotonsillitis is common and adherence to guidelines is insufficient, there is a need for a well-described, repeatable and scientifically evaluated ASP for pharyngotonsillitis.

Aims and Objectives

To scientifically develop and evaluate an ASP to see if this intervention can increase adherence to guidelines for the diagnosis and treatment of pharyngotonsillitis in primary care.

Research questions

Is there a difference between PHCCs randomized to ASP intervention or control in change from baseline and measurements after 6, 12 and 18 months regarding the following outcomes:

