1. the proportion of patients with pharyngotonsillitis prescribed antibiotics (J01 excluding methenamine) having a positive RADT for GAS? (Pharyngotonsillitis is a collective term that covers several diagnostic codes (ICD-10 codes))?
2. the proportion of patients with pharyngotonsillitis and a negative rapid test for GAS prescribed antibiotics (J01 excluding methenamine)?
3. the proportion of patients with pharyngotonsillitis prescribed recommended first-line antibiotics (in Sweden phenoxymethylpenicillin = PcV)?
4. the proportion of patients given a diagnosis of pharyngotonsillitis where CRP was analysed?

The following research questions will not estimate change but rather focus on a description of numbers during the baseline period:

5. the proportion of patients with pharyngotonsillitis prescribed antibiotics where no throat swab was taken

6. the proportion of patients given a diagnosis of pharyngotonsillitis where throat swab culture was analysed?
7. the proportion of patients given a diagnosis of pharyngotonsillitis where a rapid test for mononucleosis was analysed?

Is there a correlation between any change in the proportion of patients with antibiotic-treated (J01 excluding methenamine) pharyngotonsillitis with a positive RADT for GAS and the structural factors in the intervention group:

- the size of the PHCC (number of enlisted patients) and the age profile of enlisted patients?
- the number of patients with pharyngotonsillitis per 1000 enlisted patients and year?
- geographical location (large or mid-sized city versus small village)?
- Adjusted Clinical Group (ACG; a measure for evaluating the enlisted population's state of health)?
- Care-need index (CNI, socio-economic variables)?
- Type of PHCC: private/public?
- staffing (proportion of permanent-employed GPs, Residents, interns and locum tenens)?

Study Methods

Target and Study Population

50 PHCCs in the southwest of Sweden (Västra Götaland Region), volunteering to participate in this project, are randomized either to an intervention group, implementing the newly developed ASP for pharyngotonsillitis, or to a control group.

Inclusion criteria:

- PHCCs located in Västra Götaland with an agreement with Region Västra Götaland (there are about 200 such PHCCs).
- The PHCC has at least 3 medical practitioners (required for reflective meetings to be meaningful).
- The PHCC has an electronic medical record compatible with the data extraction tool MedRave Primary Care.

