- the proportion of patients with a formal diagnosis of pharyngotonsillitis where a rapid test for mononucleosis has been analysed

This data is extracted (for the last six months) using the software "Medrave4 Primary care ®" at baseline and after 6, 12 and 18 months. Virtually all PHCCs in Västra Götaland have this software and regularly use it for monitoring quality at the PHCC. In addition, all PHCCs included in this project will check that the rapid test for GAS is registered in the electronic medical record in such a way that the software "Medrave4 Primary Care ®" can identify this.

Structural data required in CRF:

- Staffing at the present time: Number of permanent-employed GPs, Residents, interns, and locum tenens, respectively divided into short-term (<3 months of service) and long-term (\geq 3 months of service) locum tenens.
- The number of patients with pharyngotonsillitis per 1000 patients enlisted at the PHCC at baseline.

Structural data for each participating PHCC

These are obtained from Munin (a quality monitoring software for Primary care in Västra Götaland):

- Type of PHCC: run privately or public?
- the size of the PHCC (number of enlisted patients) and age profile of enlisted patients?
- geographical location (large or mid-sized city versus small village)?
- the number of patients with pharyngotonsillitis per 1000 enlisted patients and year?
- Adjusted Clinical Group (ACG); a measure for evaluating the enlisted population's state of health)?
- Care-need index (CNI); socio-economic index of patients enlisted at the PHCC

Data processing

Descriptive statistics

Descriptive statistics (a measure of central tendency and probability distribution) will be presented for the all previously stated research questions at the start of the study (when the intervention starts at the PHCCs = baseline) and after 6, 12 and 18 months.

Comparisons at baseline

Comparative statistics (chi-two tests and t-tests pending on variable type) will be performed to identify differences between the intervention group and the control group at baseline.

Estimation of change

Any change between the data for the 6 months prior to the intervention (when the intervention starts at the PHCCs = baseline) and measurement after 6, 12 and 18 months, respectively, is calculated for each PHCC regarding the following outcome measures:

Primary outcome measure

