1. the proportion of patients with antibiotic-treated (J01 excluding methenamine) pharyngotonsillitis having a positive rapid test for GAS

Secondary outcome measures

2. the proportion of patients with pharyngotonsillitis and a negative rapid test for GAS prescribed antibiotics (J01 excluding methenamine)
3. the proportion of antibiotic-treated (J01 excluding methenamine) patients with pharyngotonsillitis treated with recommended antibiotic according to guidelines (PcV)
4. the proportion with pharyngotonsillitis diagnosis where CRP was analysed
5. the proportion of patients with pharyngotonsillitis prescribed antibiotics where no throat swab was taken
6. the proportion with pharyngotonsillitis diagnosis where throat swab culture was analysed
7. the proportion with pharyngotonsillitis diagnosis where a rapid test for mononucleosis has been analysed.

Regression analysis

A) Investigate if the intervention is effective

To investigate whether a change in outcome measure 1-4 differs between the intervention group and the control group, linear regression is performed where adjustment is made for any variables that differ at baseline. A regression is performed for each individual outcome measure at follow-up after 6, 12 and 18 months. Change in the respective outcome measures compared to baseline is used as a dependent variable. Group affiliation (intervention group or control group) will be used as an independent variable. Independent variables will also be the following covariates taken from baseline measurement: the number of enlisted patients at baseline, location in cities versus small villages, Adjusted Clinical Group (ACG), Care-need index (CNI) and type of PHCC (private/public).

B) Investigate if structural factors are associated with maintaining the effect of the intervention

To study if there is a relationship between more permanent change in the proportion of patients with antibiotic-treated (J01 excluding methenamine) pharyngotonsillitis who had a positive rapid test for GAS (primary outcome measure) and structural data in the intervention group, regression analysis will be done.

Change between baseline and follow-up data (18 months after initiation of intervention) for the proportion of patients treated with antibiotics for pharyngotonsillitis who have had a positive rapid test for GAS is used as a dependent variable. The following independent variables will be used:

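### Analysis A models change from baseline but does not prespecify the PHCC's baseline value of the outcome as a covariate, so it usually gives up precision that data already collected would recover

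*Combined protocol and SAP*

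**What the plan says.** Part A of Regression analysis specifies a separate linear regression for each of outcomes 1 to 4 at 6, 12 and 18 months.

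- Dependent variable: "Change in the respective outcome measures compared to baseline is used as a dependent variable".
- Group term: "Group affiliation (intervention group or control group) will be used as an independent variable".
- Fixed covariates: "Independent variables will also be the following covariates taken from baseline measurement: the number of enlisted patients at baseline". The list continues with city or village location, ACG, CNI and private or public ownership, five in all. The baseline value of the outcome is not listed.
- Conditional covariates: "linear regression is performed where adjustment is made for any variables that differ at baseline". The section Comparisons at baseline says how such differences are found: "Comparative statistics (chi-two tests and t-tests pending on variable type) will be performed to identify differences". It gives no significance threshold and does not say which variables are eligible.

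Under Data collection, the outcome proportions are extracted for every PHCC at baseline, so the missing covariate is already in hand. The research questions are put in terms of a difference between arms "in change from baseline and measurements after 6, 12 and 18 months regarding the following outcomes". The PHCCs "are randomized either to an intervention group, implementing the newly developed ASP for pharyngotonsillitis, or to a control group".

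**The concern.** A change score does correct for baseline, but it fixes the slope of follow-up on baseline at 1. If the variances are equal at both times, the actual slope is rho. Whenever the actual slope differs from 1, the change score carries variance that a fitted slope would remove.

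The only other way in for the baseline outcome is a significance test between randomised arms. Such a test responds to chance imbalance and says nothing about how well the variable predicts the outcome. It also leaves part of the primary model to be settled after the data are seen.

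With about 50 randomised units, the stake is power and the width of the confidence interval. Bias is not at issue.

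**Working it through.** **The plan's own figure.** The plan gives no precision or correlation figure for this analysis. Its nearest number is the 45 PHCCs in the sample-size section (Cohen's d 0.3, alpha 0.05, power 0.95). That number does not reproduce: a two-sided t-test with d = 0.3 needs 580 in total. Reading 0.3 as f-squared gives 46. This is a separate matter, and nothing below depends on it.

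**Inputs.** From the documents: 50 PHCCs, two arms, five fixed covariates, change as the dependent variable. Assumed, because the documents do not state them: 25 per arm, two-sided alpha 0.05, rho from 0.3 to 0.9, equal SDs at both times unless stated, and a 0.05 threshold for a baseline difference. Rho and SD are those remaining after the five covariates.

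**Step 1: variance.** In units of the outcome variance, the change score has variance 2(1 − rho). The baseline-adjusted outcome has 1 − rho². The ratio is (1 − rho²) / [2(1 − rho)] = (1 + rho)/2. Going from five to six covariates multiplies the adjusted variance by (47/41)/(47/42) = 42/41.

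| rho | change score | adjusted | ratio | extra PHCCs for equal precision | same, with 42/41 |
|---|---|---|---|---|---|
| 0.3 | 1.40 | 0.91 | 0.65 | 54% | 50% |
| 0.5 | 1.00 | 0.75 | 0.75 | 33% | 30% |
| 0.7 | 0.60 | 0.51 | 0.85 | 18% | 15% |
| 0.9 | 0.20 | 0.19 | 0.95 | 5% | 3% |

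The extra PHCCs are 1/ratio − 1. Simulated variance ratios, with five covariates in the model, were about 0.69, 0.79, 0.87 and 0.98.

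**Step 2: power.** Noncentral t, with 50 − 7 = 43 residual degrees of freedom for the change score and 42 with baseline added, and variance inflation 47/42 and 47/41. Each cell reads change score → adjusted.

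| rho | effect giving the change score 80% power | power at that effect | power at 0.8 SD | power at 0.3 SD |
|---|---|---|---|---|
| 0.3 | 1.015 SD | 80 → 92.9% | 60 → 77% | 13 → 17% |
| 0.5 | 0.858 SD | 80 → 89.1% | 74 → 85% | 17 → 20% |
| 0.7 | 0.664 SD | 80 → 85.1% | 92 → 95% | 24 → 27% |
| 0.9 | 0.384 SD | 80 → 81.0% | 100 → 100% | 59 → 60% |

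**Step 3: what the plan's conditional rule recovers.** A t-test at 0.05 flags the baseline outcome only if the arms differ by more than t(0.975, 48) × √(2/25) = 0.569 SD. In 10,000 simulated trials per setting this happened in 4.7 to 5.1% of trials. Simulated power at 0.8 SD for change score / plan's rule / always adjusted was 60.1/61.2/77.7%, 74.9/75.6/84.4% and 91.9/92.2/95.1% at rho 0.3, 0.5 and 0.7.

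**Step 4: a single trial.** A baseline imbalance D that is not flagged shifts the change-score estimate by −(1 − rho)D. The expected absolute imbalance is √(2/25) × √(2/π) = 0.226 SD, so the typical shift is 0.16, 0.11, 0.07 or 0.02 SD. This is the precision loss of Step 1 seen from inside one trial and is not an additional harm: 2(1 − rho) − (1 − rho²) = (1 − rho)².

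**Step 5: validity.** Under the null the mean error was at most 0.003 SD. Type I error was 4.8 to 5.3% for the change score, 4.2 to 4.9% for the plan's rule and 4.7 to 5.0% with fixed adjustment.

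**Step 6: unequal SDs.** If r is the ratio of follow-up SD to baseline SD, the variance ratio is r²(1 − rho²)/(1 + r² − 2·rho·r). It never exceeds 1 and equals 1 when r = 1/rho. At r = 0.8 it is 0.57 for rho 0.5 and 0.63 for rho 0.7. At r = 1.25 it is 0.89, 0.98 and 1.00 for rho 0.5, 0.7 and 0.8. After the 42/41 factor the last two become 1.005 and 1.024.

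**The case against.** The strongest reply is that the plan asks about change, that a change score is a valid analysis under randomisation, and that the conditional rule admits the baseline value when imbalance is greatest. The first two points are correct, but neither is an argument against adding the covariate. With baseline in the model, the group coefficient is identical whether change or the follow-up value is the dependent variable.

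The third point is partly right. At a 0.05 threshold the rule recovers about a quarter of the available variance reduction, at 0.10 about 40% and at 0.20 about 60%. Power nevertheless rises by only 1 to 3 points under any of these thresholds.

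Two points do limit the size of the claim. The gain is not guaranteed: with a follow-up SD 1.25 times the baseline SD and rho of 0.7 to 0.8 there is essentially none. And at 0.3 SD, the plan's stated effect size if read on the scale of the outcome, the gain is only 1 to 4 power points. The 0.8 SD used for illustration is an assumption.

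**Conclusion.** The point holds, as a free improvement to precision and not as a threat to validity. The baseline value of the outcome is not a prespecified covariate in part A, and the test-driven rule does not make up for that. With equal variances and 25 PHCCs per arm, adjustment removes 35%, 25%, 15% or 5% of the large-sample variance at rho 0.3, 0.5, 0.7 or 0.9.

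The omission is certain from the text. The magnitude is not, since rho, the SD ratio, the allocation ratio and the threshold are all absent from the documents. With equal variances, break-even after the lost degree of freedom comes only at rho of about 0.95 to 0.96. A correlation that high cannot be presumed for four outcomes at three times, particularly as the 6- and 18-month windows cover the opposite half of the year from the baseline window. The largest loss found in the settings examined is about 2% in variance.

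**What to change.** In every part A regression (outcomes 1 to 4 at 6, 12 and 18 months), name the PHCC's baseline value of the outcome being analysed as a fixed covariate beside the five already listed. Change can remain the dependent variable, so the research question stands as written.

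Delete the clause that adjusts for variables found to differ at baseline, and keep the baseline comparison descriptive. This deletion can be separated from the first step: adding the covariate alone restores the precision, while the deletion fixes the model in advance.

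The cost is a change of wording in the analysis section and one residual degree of freedom (43 to 42 with 50 PHCCs). No new data are needed.
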